Days from randomization	≤30	—	15	29	43	57	71	85	99	113	N/A		
Visit interval tolerance (days)		—	±3	±3	±3	±3	±3	±3	±3	±3	N/A	±3	
Prior treatments for AD	X												Includes medications and procedures.
Concomitant therapies	X	X	X	X	X	X	X	X	X	X	X	X	Includes medications of special interest such as TCS and TCI and procedures.
Adverse events (AEs)	X	X	X	X	X	X	X	X	X	X	X	X	Collection for AEs associated with vaccinations will begin at Week 12. For AESIs, additional data are collected (Section 8.3.6).
Physical Evaluation													
Height	X									X			

Notes:												

 Visit 1 procedures may be conducted over more than 1 day as long as all activities are completed within the allowable visit tolerance. For early terminations (ETs) that occur before the last visit in treatment period, see the activities listed for ET in this table. Visit 801 is only for study participants who are terminating early or not rolling into the long-term extension study (DRM06-AD07/J2T-DM-KGAA). 												
Visit number	1	2	3*	4	5*	6*	7*	8	9*	10	ET	V801*
Weeks from randomization	Screening (-4)	Baseline /Day 1	2	4	6	8	10	12	14	16	ET	Safety follow-up Week 26 (or approximately 12 weeks after last study drug injection)
Days from randomization	≤30	—	15	29	43	57	71	85	99	113	N/A	* = visit may be conducted remotely or on site, per preference of the study site or participant. See Section 4.1 for details about remote visits.
Visit interval tolerance (days)		—	±3	±3	±3	±3	±3	±3	±3	±3	N/A	±3
Weight	X									X	X	
Vital signs	X	X		X			X		X	X	X	See Section 8.2.2 for details.
Physical examination	X									X	X	See Section 8.2.1 for details. Additional symptom-directed physical examinations may be conducted at the discretion of the investigator.

Notes:												

 Visit 1 procedures may be conducted over more than 1 day as long as all activities are completed within the allowable visit tolerance. For early terminations (ETs) that occur before the last visit in treatment period, see the activities listed for ET in this table. Visit 801 is only for study participants who are terminating early or not rolling into the long-term extension study (DRM06-AD07/J2T-DM-KGAA). 												
Visit number	1	2	3*	4	5*	6*	7*	8	9*	10	ET	V801*
Weeks from randomization	Screening (-4)	Baseline /Day 1	2	4	6	8	10	12	14	16	ET	Safety follow-up Week 26 (or approximately 12 weeks after last study drug injection)

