[22] Have presence of skin comorbidities that may interfere with study assessments.

[23] Have a history of malignancy, including mycosis fungoides, within 5 years before screening (Visit 1), except completely treated in situ carcinoma of the cervix or completely treated and resolved non-metastatic squamous or basal cell carcinoma of the skin with no evidence of recurrence in the past 12 weeks.

[24] Have a severe concomitant illness(es) that in the investigator's judgement would adversely affect the patient's participation in the study. Have any other medical or psychological condition that in the opinion of the investigator may suggest a new and/or insufficiently understood disease, may present an unreasonable risk to the study participant because of his/her participation in this clinical trial, may make patient's participation unreliable, or may interfere with study assessments.

[25] Have a prior history of Guillain-Barre syndrome.

[26] Are allergic to latex.

[27] Have a history of past vaccination allergy or Arthus-type hypersensitivity.

- [28] Have an uncontrolled seizure disorder.
- [29] Have known hypogammaglobulinemia or a screening serum immunoglobulin G (IgG) or immunoglobulin A (IgA) concentration less than the lower limit of the reporting laboratory's reference range.

Prior/Concomitant Therapy and Vaccines

- [30] Have been treated with TCS, calcineurin inhibitors, or phosphodiesterase-4 inhibitors such as crisaborole within 1 week prior to the baseline visit (randomization; Visit 2).
- [31] Have been treated with any of the following agents within 4 weeks prior to the baseline visit (randomization; Visit 2):
 - a. Immunosuppressive/immunomodulating drugs (e.g., systemic corticosteroids, cyclosporine, mycophenolate-mofetil, interferon gamma(IFN- γ), Janus kinase inhibitors, azathioprine, methotrexate, etc.)
 - b. Phototherapy and photochemotherapy (PUVA) for AD
- [32] Have been treated with the following prior to the baseline visit (randomization; Visit 2):
 - a. An investigational drug within 8 weeks or within 5 half-lives (if known), whichever is longer
 - b. B Cell-depleting biologics, including rituximab, within 6 months
 - c. Other biologics within 5 half-lives (if known) or 8 weeks, whichever is longer
- [33] Have used prescription moisturizers within 7 days of the baseline visit (randomization; Visit 2).

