7.1.2. Criteria for Permanent Discontinuation of Study Drug

In rare instances, it may be necessary for a participant to permanently discontinue (definitively discontinue) study drug.

Possible reasons for permanent discontinuation of study intervention

Possible reasons that may lead to permanent discontinuation of the study drug include, but are not limited to, the following:

Investigator decision

- The investigator decides that the participant should be discontinued from study drug. Some examples may include:
 - Inter-current illness that would, in the judgment of the investigator, affect assessments of clinical status to a significant degree
 - Treatment-related AEs that are clinically significant, deemed persistent, in the judgment of the investigator
 - Unacceptable toxicity

Systemic hypersensitivity reaction

- If the investigator, after consultation with the sponsor-designated medical monitor, determines that a systemic hypersensitivity reaction has occurred related to study drug administration, the participant should be permanently discontinued from the study drug.
- If a participant experiences a hypersensitivity event determined by the investigator to relate to the vaccine products, the participant will not be permanently discontinued from the study drug.

Required reasons for permanent discontinuation of study intervention

Permanent discontinuation of study drug should occur in the following instances:

Use of systemic rescue treatment

- If a participant receives rescue treatment with a systemic corticosteroid, immunosuppressant, or phototherapy, the participant must permanently discontinue study drug.
- Participants who receive rescue treatment with topical steroids may continue treatment with study drug.

NOTE: Participants who discontinue study drug due to rescue medication use should continue to attend all study visits through Week 16 and be assessed for safety and efficacy according to the SoA (as shown in the table at the end of this subsection).

Hepatic event or liver test abnormality

- Participants who are discontinued from the study drug due to a hepatic event or liver test abnormality should have additional hepatic safety data collected via eCRF. Discontinuation of the study drug for abnormal liver tests **should be** considered by the investigator when a participant meets one of the following conditions after consultation with the sponsor-designated medical monitor (see Section 8.2.7):
 - ALT or AST ≥ 8 times ULN

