Appendix 2. Definition of Rescue Medications

The AD rescue therapy in this study is defined as: high-potency TCS and systemic AD therapy. The topical treatments and systemic treatments are defined as following:

1. Topical AD Treatment (including TCSs, TCI, and crisaborole)

Route of topical treatments includes: Topical and Transdermal.

TCS: ATC code is D07

High Potency TCS: ATC codes are D07AC or D07AD

Low or moderate potency TCS: ATC code is D07, excluding D07AC or D07AD

TCI: PT includes: TACROLIMUS, PIMECROLIMUS

Crisaborole: PT includes: CRISABOROLE

2. Systemic AD Treatment (including systemic corticosteroids, immunosuppressant, biologics, and phototherapy/PUVA)

Route of systemic treatments administration includes: Oral, Intra-Arterial, Intramuscular, Intraperitoneal, Intravenous, Subcutaneous, and Transdermal. (This condition applies to the following categories except for phototherapies.)

Systemic Corticosteroids: ATC code is H02

Immunosuppressant: Defined as: ATC2 is L04 or PTs of Abrocitinib or Ruxolitinib excluding PTs mentioned in Biologics

Biologics: Defined as following PTs:

Infliximab, Infliximabum, Etanercept, Etanerceptum, Adalimumab, Adalimumabum, Certolizumab, Certolizumabum, Certolizumab pegol, Golimumab, Golimumabum, Ozoralizumab, Afelimumab, Afelimumabum, Tumor Necrosis Factor Alpha (TNF-) Inhibitors, Tabalumab, Tregalizumab, Anakinra, Basiliximab, Basiliximabum, Daclizumab, Daclizumabum, Tocilizumab, Tocilizumabum, Mepolizumab, Mepolizumabum, Rilonacept, Rilonaceptum, Ustekinumab, Canakinumab, Briakinumab, Fezakinumab, Sirukumab, Sarilumab, Lebrikizumab, Secukinumab, Olokizumab, Gevokizumab, Brodalumab, Ladarixin, Ixekizumab, Dupilumab, Tildrakizumab, Tildrakizumabum, Reslizumab, Reslizumabum, Guselkumab, Guselkumabum, Olamkicept, Fletikumab, Bimekizumab, Mirikizumab, Risankizumab, Abatacept, Ligelizumab, Vedolizumab, Belimumab, Nemolizumab, Tralokinumab, Omalizumab

Phototherapy or PUVA:

Programming search of medication name (actual term or PT) contains 'photo' then medicals to manually review to confirm whether the medication in question is indeed 'Phototherapy' or 'Photochemotherapy'.

Appendix 3. Details of Combining Estimates and Test Statistics for Categorical Endpoints with Multiple Imputation

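### SAP Appendix 2 finds phototherapy/PUVA rescue only through the string 'photo', so some PUVA or UV entries can go unflagged; the exposure is limited but cheap to close

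*SAP*

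**What the plan says.** SAP Appendix 2 defines rescue as high-potency topical corticosteroid or systemic AD therapy. The systemic group is headed "Systemic AD Treatment (including systemic corticosteroids, immunosuppressant, biologics, and phototherapy/PUVA", so phototherapy and PUVA are rescue by definition. The other systemic groups are found by ATC code or a list of preferred terms. Phototherapy and PUVA are found by a text search: "Programming search of medication name (actual term or PT) contains" the string `photo`. The next step is for "medicals to manually review to confirm whether the medication in question is indeed" phototherapy or photochemotherapy. No other string, code or data source is named, and the SAP does not say whether the search ignores case.

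The trial uses PUVA as its own short form: Protocol 5.2 lists "Phototherapy and photochemotherapy (PUVA) for AD". In the Schedule of Activities (Protocol 1.3), the comment on the concomitant-therapies row reads "Includes medications of special interest such as TCS and TCI and procedures". Protocol 6.5.3 requires rescue use to be captured in the eCRF but gives no form or term for phototherapy.

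Protocol 7.1.2 adds a safeguard: "If a participant receives rescue treatment with a systemic corticosteroid, immunosuppressant, or phototherapy, the participant must permanently discontinue study drug". SAP 6.2 treats permanent treatment discontinuation as an intercurrent event separate from rescue.

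**The concern.** The item is titled for phototherapy or PUVA, yet the word PUVA does not contain the search string. Nor do the usual ways of writing UV treatment without the word phototherapy. Because the manual step only confirms hits, it can remove false positives but cannot restore a record that was never returned.

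The rescue flag is used widely. It sets values to baseline in the hybrid analysis (SAP 6.4.1), to missing for MMRM and LOCF (6.4.2, 6.4.3) and to non-response under NRI (6.4.4). It is a ground for exclusion from the per-protocol set (PPS) used for the primary vaccine analysis (6.1.1). It also defines the rescue and flare summaries (Section 4, 6.9). A missed record could therefore be handled wrongly in several places.

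**Working it through.** The rule has no stated figure to reproduce. The check has four parts.

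**1. String test.** Plausible entries were tested for `photo`.

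| Entry | Exact case | Ignoring case |
|---|---|---|
| PUVA; PUVA therapy | no | no |
| UVB; NB-UVB; narrowband UVB; UVA1 | no | no |
| light therapy; ultraviolet light treatment | no | no |
| Phototherapy; Photochemotherapy | no | yes |
| UVB phototherapy; PUVA (photochemotherapy) | yes | yes |

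The rule searches the reported term or the PT, so an entry in the first three rows is lost only if its PT also lacks the string. The documents do not show how these terms are coded.

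**2. Following a missed flag through the analyses.**

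| Use (SAP section) | Flag works | Flag missed, stop recorded | Flag missed, no stop recorded |
|---|---|---|---|
| NRI (6.4.4) | non-response | non-response | observed score kept |
| MMRM, LOCF (6.4.2, 6.4.3) | later values missing | later values missing | observed score kept |
| Hybrid MCMC-MI, stop coded lack of efficacy (6.2.2, 6.4.1) | baseline | baseline | not applicable |
| Hybrid MCMC-MI, other or no stop reason | baseline | missing, then imputed from own arm | observed score kept |
| Percentage rescued, time to first rescue, flare (4, 6.9) | counted | not counted | not counted |
| PPS (6.1.1) | excluded | see part 3 | see part 3 |

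**3. PPS.** Planned injections (Protocol 6.1.1: 250 mg syringes, 500 mg at baseline and Week 2, 250 mg at Weeks 4 to 14): 2 + 2 + 6 = 10.
- Stop before Week 12: no vaccines are given (Protocol 6.1.2, 7.1.2). The PPS requires both vaccines, so the participant leaves it whatever the search finds.
- Stop after the Week 12 dose: 9/10 = 90%, above the 80% PPS threshold. Both vaccines have been given, and Protocol 7.1.2 keeps participants who stop for systemic rescue in the study through Week 16. Only the rescue criterion or the separate deviation tracking (SAP 6.1.1, 6.15) would exclude them.
- Phototherapy started after the Week 14 dose: 10/10 = 100%. No planned dose remains to be stopped, and the documents do not say whether a discontinuation would be recorded.

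**4. Size.** Planned numbers per arm are 240/2 = 120 randomised and 218/2 = 109 per protocol.
- One non-responder turned responder: 1/120 = 0.83 points; 1/109 = 0.92 points.
- If 1 to 5 cases flipped in one arm of 120 (an assumed range): 1/120 to 5/120 = 0.83 to 4.17 points.
- In the hybrid analysis with a recorded stop, setting to baseline gives non-response in all 25 datasets. Imputation gives response in a fraction q of them, so one case moves the arm by q/120. With q anywhere from 0 to 1, that is 0 to 0.83 points.
- For the vaccine endpoints, the planned 90% half-widths (Protocol 9.2) are 1.645 × √(2 × 0.83 × 0.17/109) = 0.084 and 1.645 × √(2 × 0.90 × 0.10/109) = 0.067. One participant wrongly kept in the PPS shifts an arm by at most about 0.9 points against roughly 8 and 7.

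The modified ITT set drops two sites of unstated size, so its arms may be smaller than 120 and each case may weigh slightly more than 0.83 points.

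**The case against.** The strongest reply is that the harm mostly needs a second failure. Phototherapy obliges a permanent stop, the stop is captured independently of Appendix 2, and three of the four missing-data methods then give the intended result. This stands. A reader might infer that a missed phototherapy user simply keeps treated skin and itch scores as a study-drug response. The documents support that only where no stop is recorded.

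A reader might also infer that the primary vaccine analysis is generally contaminated. It is not. Stops before Week 12 leave the PPS through the vaccine requirement, and later ones may still be caught by the deviation tracking. Nothing says PPS exclusion rests on the text search alone.

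Two further inferences go beyond the documents. The first is that procedure records are certainly missed. The rule says medication name and the Schedule of Activities mentions procedures, but no document shows where phototherapy is entered or whether a separate procedure dataset exists. The second concerns the route lists. The topical list is "Route of topical treatments includes: Topical and Transdermal" and the systemic list ends "Intravenous, Subcutaneous, and Transdermal", so a permitted topical might seem liable to count as systemic rescue. That would also need the product to carry an L04 or H02 code, and the dictionary coding is not shown. The overlap is real; an error from it is not demonstrated.

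The reply does not cover the hybrid analysis when the stop reason is not lack of efficacy, the rescue and flare summaries, the Week 12 to 16 window, or participants without a recorded stop.

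**Conclusion.** The search rule as written can miss phototherapy or PUVA rescue, and its review step cannot correct that. The exposure is confined to four places: the hybrid MCMC-MI analysis, where some cases are imputed instead of set to baseline; the rescue percentage, time-to-rescue and flare summaries; PPS membership for phototherapy started between Weeks 12 and 16, unless the deviation tracking catches it; and anyone with no recorded stop.

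The effect is probably small: at most about 0.8 to 0.9 points in one arm per flipped responder, with an unknown number of cases. This assumes planned arm sizes and that some entries lack the string in both reported term and PT. The direction of bias is not documented. A reader might expect rescue to be commoner on placebo, so that misses dilute the efficacy difference, but neither document gives rescue rates by arm.

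**What to change.** In SAP Appendix 2:
- State that the search ignores case, and add `PUVA`, `UVA`, `UVB`, `ultraviolet`, `psoralen`, `excimer` and `light therapy` to `photo`. Match `UVA` at the start of a word; otherwise names such as rosuvastatin are returned.
- Apply the search to all concomitant-therapy records, including any procedure entries.
- Reconcile the flags against participants recorded as stopping study drug for systemic rescue, and query mismatches in either direction.
- Optionally, add one sentence that records already classed as topical corticosteroid or calcineurin inhibitor are not also counted as systemic.

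SAP Version 3 was approved after the Week 16 lock (SAP Section 3), so the added records should be reviewed blind to arm and the number of changed flags reported. If none change, that settles the point. The cost is a few lines of text and code and manual review of a few more records.

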9.1. Statistical Hypotheses

Study KGAK is a descriptive study with no planned hypothesis testing. Confidence intervals (CIs) will be used to compare seroresponses for lebrikizumab- and placebo-treated participants.

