Abbreviations: AD = atopic dermatitis; ADA = antidrug antibody; AE = adverse event; EASI = Eczema Area and Severity Index; EASI 90 = $\geq 90\%$ reduction from baseline in EASI score; eCRF = electronic case report form; hSBA = human complement serum bactericidal assay; ICH = International Council for Harmonisation; IgG = immunoglobulin G; ITT = intent-to-treat; MCMC-MI = Markov chain Monte Carlo multiple imputation; mITT = modified intent-to-treat; NRS = numerical rating scale; POEM = Patient-Oriented Eczema Measure; PPS = per-protocol set; PROMIS = Patient-Reported Outcomes Measurement Information System; PSAP = program safety analysis plan; TE-ADA = treatment-emergent antidrug antibody.

SAP Version 3 was approved after Week 16 database lock (DBL) and before final DBL.

Revisions in SAP Version 3 include:

Section	Description of Change	Rationale
Sections 4, 5.2, 6.10, 6.10.1	Replaced hSBA with rSBA.	At the time of Week 16 DBL, the MCV hSBA data collected and processed by Eurofins was considered invalid because the assay procedure was not successfully validated. Personnel who have access to the patient-level data have no access to the biospecimen for the MCV hSBA. For final analysis, Lilly has identified Nexelis as an alternate vendor for analyzing the MCV response using a fully validated rSBA to deliver results for the final DBL and for analysis.
Section 6.16	Added detailed description of MCV response data issue observed at Week 16 DBL. Added the solution of MCV response data issue and discussed the impact to Week 16 DBL and final DBL.	The same as above.

Abbreviations: DBL = database lock; hSBA = human complement serum bactericidal assay; MCV = Meningococcal (Groups A, C, Y, and W-135) Oligosaccharide Diphtheria CRM197 Conjugate Vaccine; rSBA = rabbit complement serum bactericidal assay.

4. Study Objectives

Table KGAK.4.1 shows the protocol-defined objectives and endpoints of the study. In addition, the analysis of some nonprotocol-defined endpoints is described in Section 6.10 to provide supportive evidence of efficacy.

Table KGAK.4.1. Protocol-Defined Objectives and Endpoints

Objectives	Endpoints
Primary	

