- The estimated common risk difference along with 95% CIs. The common risk difference is the difference in proportions adjusted for the stratification factors as mentioned in Section [6.3](#). SAS PROC FREQ will be used for the estimates and CIs, where the CIs are calculated by using Mantel-Haenszel-Sato method (Sato 1989)
- Cochran-Mantel-Haenszel (CMH) test will be used to compare the treatment groups while adjusting for the stratification factors. The CMH p-value and the CMH adjusted odds ratio (OR) along with the 95% two-sided asymptotic (that is, not continuity corrected) CIs will be reported

Treatment comparisons of key continuous efficacy variables and health outcome variables at each postbaseline time point will be made using analysis of covariance (ANCOVA) with the following in the model: treatment group, baseline value, and stratification factors mentioned in Section [6.3](#). Type III tests for least squares (LS) means will be used for statistical comparison between treatment groups. The LS mean difference, standard error (SE), p-value, and 95% CI, unless otherwise specified, will also be reported.

Treatment comparisons of other continuous efficacy variables and health outcome variables with multiple postbaseline measurements will be made using mixed-model for repeated measures (MMRM). When MMRM is used, the model includes treatment, baseline value, visit, the interaction of the baseline value-by-visit, the interaction of treatment-by-visit, and the stratification factors mentioned in Section 6.3 as fixed factors. The covariance structure to model the within-participant errors will be unstructured. If the unstructured covariance matrix results in a lack of convergence, the heterogeneous Toeplitz covariance structure, followed by the heterogeneous autoregressive covariance structure, will be used. The restricted maximum likelihood (REML) will be used. The Kenward-Roger method will be used to estimate the denominator degrees of freedom. Type III tests for the LS means will be used for the statistical comparison; the 95% CI will also be reported.

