Following the implementation of MCMC-MI imputation as specified in Section 6.4.1, the 25 data sets with imputations should be set together and sorted by imputation number. The following sections describe the processes for combining inferences for the individual imputed data sets into 1 inference for reporting. All calculations are performed in SAS Software Version 9.4.

Summarize Unadjusted Response Rate

The response rates, overall and by treatment arm, and their associated SEs are computed for each imputed data set using PROC FREQ with the *riskdiff* option specified for the appropriate column in the TABLES statement. The response rates and SEs from the resulting output are combined across the 25 imputed data sets using PROC MIANALYZE, separately for each arm and the overall group.

Note that the estimate and 95% CI bounds output by PROC MIANALYZE are percentages (that is, they are in terms of the response rate). To obtain the number of responders, the estimated percentage is multiplied by the number of individuals in the analysis population and rounded to the nearest integer.

Compute Stratified Measures of Association

The common risk difference, common OR, and CMH test statistic are computed for each imputed data set using PROC FREQ with the *riskdiff* option for the appropriate column (for risk difference) and the *cmh* option (for OR and CMH test statistic) specified in the TABLES statement. Each of these analyses are stratified by geographic region, age group, and baseline disease severity via inclusion of these variables in the TABLES statement with the treatment and outcome variables.

Note that the PROC FREQ output corresponding to the Mantel-Haenszel method is used for the risk difference, and the output corresponding to the General Association statistic is used for the CMH statistic. PROC MIANALYZE is then called separately for each of these measures, with further details in the sections below.

Common Risk Difference

No transformation is necessary before using PROC MIANALYZE to combine the risk difference estimates and their associated SEs across the 25 imputed data sets. This procedure outputs an estimate of the common risk difference and the associated 95% CI bounds.

Common OR

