The OR from each imputed data set is first transformed using the natural logarithm. The SE for each log OR (SE_{lOR}) is derived from the OR 95% CI bounds (LB_{OR} , UB_{OR}) according to the following equation: $SE_{lOR} = (\ln(UB_{OR}) - \ln(LB_{OR}))/ (2 * 1.96)$. The log OR and derived SE are then combined using PROC MIANALYZE, which outputs a combined estimate of the log OR and the associated 95% CI. Finally, these measures can be exponentiated to transform them back to the OR scale.

CMH Test

The CMH test statistic (CMH) from each imputed data set is transformed using the Wilson-Hilferty transformation and standardized so that it has approximately a standard normal distribution (Ratitch et al. 2013). In particular, the transformed CMH statistic is computed as

$$CMH_{WH} = \left(\frac{CMH}{df} \right)^{\frac{1}{3}} - \frac{1 - \frac{2}{9*df}}{\sqrt{\frac{2}{9*df}}},$$

where df is the degrees of freedom of the CMH statistic. Then the SE for each CMH_{WH} is 1, and PROC MIANALYZE is used to output a combined estimate of the transformed CMH statistic. Note that the 2-sided p-value output by PROC MIANALYZE is not used directly, but instead the 1-sided p-value is computed manually using both the t statistic and 2-sided p-value output by PROC MIANALYZE; if t statistic is >0 , then the 1-sided p-value is computed as one half of the 2-sided p-value; otherwise, the 1-sided p-value is computed as one half of the 2-sided p-value. The resulting 1-sided p-value is reported as the pooled p-value for the CMH test.

Signature Page for VV-CLIN-075212 v1.0

Approval	PPD Statistician 05-Dec-2022 00:22:51 GMT+0000
----------	--

Signature Page for VV-CLIN-075212 v1.0

Approved on 05 Dec 2022 GMT

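### SAP Appendix 3 gives the same p-value formula for both signs of the pooled CMH statistic, so when the arms are alike the reported p-value is about 1 − p and can never exceed 0.50

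*SAP*

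**What the plan says.** SAP section 6.1.2 commits to reporting, for the secondary and other binary endpoints, "The CMH p-value and the CMH adjusted odds ratio (OR) along with the 95% two-sided asymptotic" confidence limits. Where the data are multiply imputed, Appendix 3 says how the CMH p-value is pooled. The statistic from each of the 25 imputed data sets is "transformed using the Wilson-Hilferty transformation and standardized so that it has approximately a standard normal distribution", given a standard error of 1, and combined in PROC MIANALYZE.

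The two-sided p-value from that procedure is not used directly; a one-sided value is derived from it and the sign of t. For t above 0 the rule is half the two-sided value, and the text continues: "otherwise, the 1-sided p-value is computed as one half of the 2-sided p-value". It then says: "The resulting 1-sided p-value is reported as the pooled p-value for the CMH test".

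No other part of the SAP or protocol gives a different rule for t at or below 0.

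**The concern.** A condition whose two outcomes are identical does nothing, so one branch must be wrong. A large CMH statistic is evidence of a difference in either direction, so the right p-value is the upper tail of the transformed statistic. That is half the two-sided value when t is positive and 1 minus that half when t is zero or negative. The SAP's second branch returns the lower tail instead.

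The affected outputs are the rows of Table KGAK.6.7 that use CMH with MCMC-MI: IGA 0/1, IGA 0, EASI 50/75/90, and the Pruritus, Sleep-loss and Skin Pain responders, at Week 16 and at each scheduled visit. Where the arms are nearly alike, the p-value would be misleadingly small. The ordering would also reverse, so that a smaller difference gets a smaller p-value.

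**Working it through.** The SAP gives no numerical result for this rule, so there is no figure to reproduce. The check applies the rule as written and compares it with the upper tail.

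**Inputs.** 25 imputations (SAP 6.4.1). General Association statistic (Appendix 3), so df = 1 for two arms and a binary response. The standardised Wilson-Hilferty form is used, as the text's description and the standard error of 1 imply.

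**Formulas, one data set or no between-imputation variance.**
- z = [CMH^(1/3) − 7/9] / √(2/9)
- SAP rule: p = P(Z > |z|), whatever the sign of z
- Correct rule: p = P(Z > z)

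**Where the branches part.** z = 0 at CMH = (7/9)³ = 0.4705. Below that, the SAP value is exactly 1 minus the correct Wilson-Hilferty p-value. It is only approximately 1 minus the exact chi-square p-value, with a gap of up to 0.05 near CMH = 0. With no true difference, P(χ²₁ < 0.4705) = 0.507. Half of any p-value is at most 0.50, which gives the ceiling.

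| CMH | Chi-square p | z | Correct rule | SAP rule |
|---|---|---|---|---|
| 0 | 1.0000 | −1.650 | 0.9505 | 0.0495 |
| 0.01 | 0.9203 | −1.193 | 0.8835 | 0.1165 |
| 0.10 | 0.7518 | −0.665 | 0.7471 | 0.2529 |
| 0.30 | 0.5839 | −0.230 | 0.5909 | 0.4091 |
| 1.00 | 0.3173 | 0.471 | 0.3187 | 0.3187 |
| 3.84 | 0.0500 | 1.672 | 0.0472 | 0.0472 |

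**Worked counts.** Assume 109 per arm (the planning figure in SAP 5.2; the mITT size is not given) and a single stratum. With r total responders and difference d, CMH = (d/2)² / [r(218 − r)/(4 × 217)].
- 41 v 40: 0.25 / (81 × 137/868) = 0.0196; chi-square p 0.889, correct rule 0.860, SAP rule 0.140
- 45 v 40: 6.25 / (85 × 133/868) = 0.480; SAP rule 0.496
- 51 v 40: 30.25 / (91 × 127/868) = 2.272; SAP rule 0.127

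A gap of one responder therefore looks much like a gap of eleven, and a gap of five looks weaker than either.

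**With imputation noise.** Rubin pooling uses T = 1 + (1 + 1/25)B and t = mean(z)/√T, where B is the between-imputation variance. A null simulation used 20,000 runs per setting, 25 imputations and two equal IGA strata. All settings were assumed: 100 or 120 per arm, 15% or 30% response in both arms, and 4, 12 or 24 missing per arm.
- t at or below 0 in 45% to 52% of runs.
- In those runs, a median correct p of 0.62 to 0.74 is reported as 0.26 to 0.38.
- Smallest reversed p: 0.085–0.097 with 4 missing per arm, 0.135–0.142 with 12, and 0.185–0.199 with 24.
- Rate of p < 0.05: 0.050 to 0.056, identical under both rules.

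For a single data set under no difference, the rate of p < 0.05 is 0.0529 under the SAP rule against 0.0528 under the correct one. The rate of p < 0.10 is 0.162 against 0.104, and of p < 0.20 it is 0.389 against 0.203.

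**The case against.** The best case for leaving this as minor has four parts.

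1. **It is an evident slip, and the programs may be right.** That is possible, but the documents do not show the programs. The revision history says Appendix 3 was added in Version 2 to give technical detail on MCMC-MI, so a programmer or validator would work from this text. The error is still there in Version 3.

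2. **The sharpest examples ignore imputation variance, although the rule exists only for imputed data.** This stands. SAP 5.2 plans 240 randomised and 218 evaluable, a loss of about 22/2 = 11 per arm, though not all of that would be missing data. In the nearest simulated setting (12 missing per arm) the smallest reversed p was 0.135 to 0.142, so the typical distortion is between two clearly non-significant values.

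3. **Half of comparisons are reversed only if there is no true difference.** This also stands. At 109 per arm, a single stratum and assumed placebo rates of 10% to 30%, CMH falls below 0.4705 in about 7% to 17% of comparisons at a true 10-point difference, 1% to 5% at 15 points, and under 1% at 20 points. The documents give no efficacy effect size. The problem therefore lies mainly where the arms differ little, such as early visits or rare responses.

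4. **No decision turns on these values.** Protocol 9.1 states: "Study KGAK is a descriptive study with no planned hypothesis testing". The same tables carry crude proportions, risk differences and odds ratios with intervals. The nonresponder-imputation analyses, planned for several of the same endpoints, need no pooling. All of this is true and limits the harm, but it does not make the reported p-values correct. A reader would see p-values that disagree with the estimates beside them.

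**Conclusion.** The rule is wrong as written and nothing else in the documents corrects it. For t at or below 0 the reported pooled CMH p-value is exactly 1 minus the correct Wilson-Hilferty value, and no reported value can exceed 0.50. With df = 1 and no between-imputation variance this applies to every CMH below 0.4705.

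The harm is misleading, reversed p-values where the arms are alike. It is not a material rise in false significance. A value below 0.05 in the reversed region, down to the limiting 0.0495, needs CMH to be essentially 0 in every imputed data set. For t above 0 nothing changes. The co-primary Newcombe intervals, the pooled risk differences and the pooled odds ratios do not use this rule.

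The thresholds and single-data-set figures assume the standard Wilson-Hilferty form; the 0.50 ceiling does not depend on it. The simulated ranges depend on the assumed arm sizes, response rates and missingness. The correction should be made because it is nearly free and puts wrong reported values right.

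**What to change.** Change the second branch to 1 minus one half of the two-sided p-value. Confirm that the programs do this, and check any Week 16 outputs already produced. Affected p-values can be re-derived from the stored t statistic and two-sided p-value without re-running the imputations. No estimate or confidence interval changes.

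The revision history states: "SAP Version 3 was approved after Week 16 database lock (DBL) and before final DBL". The change should therefore be recorded as an error correction in the SAP or the clinical study report.

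Two housekeeping checks in the same appendix carry no weight in the conclusion above:
- Check the transformation formula against the original document, since the grouping seen here may be a PDF-reading fault. The whole difference, not only its second term, must be divided by √(2/(9df)).
- The sentence "Each of these analyses are stratified by geographic region, age group, and baseline disease severity" should name baseline IGA severity alone, in line with SAP 6.3. No numerical effect is expected in a US-only adult study.

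The cost is one phrase, one formula check and one wording edit, plus the program and output check.
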